### 1.1. SAMPLE SIZE CALCULATION

Patient population was determined based on mean Harris Hip Score (HHS) at 2 years follow-up.

Sample size calculation was led as follows:

$$N = \frac{4 \times \text{STD}^2 \times (Z)^2}{(X - Y)^2}$$

Where:

STD = Standard Deviation

X-Y = Margin of Error or Precision

Z = Z1- $\alpha/2$

In order to determine Harris Hip Score with 95% confidence: then Z = 1.96

If HHS is between 95 to 100: then X=100 and Y=95

Estimate standard deviation of HHS at follow-up = 13

This value has been based on results from previous studies (Reference 1)

$$N = \frac{4 \times (13)^2 \times (1.96)^2}{(100 - 95)^2}$$

N = 104

With attrition rate of 15%

Starting population = N/0.85 = 104/0.85 = 122 rounds to 125 subjects in GTS standard group.

The same calculation applied to GTS varized group.

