**NCT02851992**

TITLE	A prospective study to evaluate long-term clinical outcomes of the Global Tissue Sparing GTS® cementless femoral stem
AIMS	The objective of this prospective clinical study is to obtain multi-center, long-term (10-year) clinical data on the new GTS® femoral stem in its standard and lateralized versions as part of Post Market Surveillance requirements
DESIGN	This is a multicenter, non-controlled, prospective study. 250 subjects (GTS standard and lateralized) will be recruited. Study will be conducted in 5 centers across Europe (Germany, Italy, Spain, France)
OUTCOME MEASURES	
Primary Outcome Measure for all study patients
 
 
Mean Harris Hip Score (HHS) at 2 year postoperative
 
 
Secondary Outcome Measures for all study patients
 
 
Radiographic Evaluation: stability, incidence of radiolucencies around the prosthesis and bone remodeling
 
Patient satisfaction: EQ5D quality of life
 
Adverse Events/Complications (including revisions/removals).
 
Survivorship
 

POPULATION	250 subjects suitable for GTS femoral stem (standard and lateralized) can be included

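### Does calling X-Y the margin of error in section 1.1 misstate the precision of the primary outcome?

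*Combined protocol and SAP*

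**What the plan says.** The synopsis, under Outcome Measures, names as primary "Mean Harris Hip Score (HHS) at 2 year postoperative". Section 1.1 takes that mean as the basis for the sample size. Its formula is N = 4 × STD² × Z² / (X − Y)², and the denominator term is defined by "X-Y = Margin of Error or Precision".

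The inputs follow in the same section:

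- confidence level: "In order to determine Harris Hip Score with 95% confidence: then Z = 1.96"
- interval: "If HHS is between 95 to 100: then X=100 and Y=95"
- spread: "Estimate standard deviation of HHS at follow-up = 13"

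The result is 104 evaluable patients. Division by 0.85 for 15% attrition gives 122, which is rounded to 125 for the standard stem. For the other stem version the section says "The same calculation applied to GTS varized group". Two groups of 125 make up the 250 subjects in the synopsis.

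**The concern.** The usual formula for estimating one mean to within a margin E is N = (Z × SD / E)², where E is the half-width of the interval. It contains no factor of 4. The plan's formula has that factor and still calls X − Y a margin of error, so label and formula do not agree under the conventional meaning of the term.

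Two misreadings could follow. Someone who trusts the label would think the study was designed for ±5 points, when the design gives about ±2.5. Someone who recalculates N from the label would get about a quarter of the stated number and might conclude that the study was four times too large. Section 1.1 is the only place where the plan puts a figure on the precision of its primary outcome, so the point deserved a check.

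**Working it through.** **Inputs, all from section 1.1:** SD = 13, Z = 1.96 (two-sided 95%), X − Y = 100 − 95 = 5, attrition 15%.

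**Step 1: reproduce the plan's figure.**

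N = 4 × 13² × 1.96² / 5² = 4 × 169 × 3.8416 / 25 = 2596.92 / 25 = 103.88, rounded up to 104. This agrees with the plan.

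**Step 2: find what X − Y stands for.**

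Put E = (X − Y)/2 into N = (Z × SD / E)². This gives N = 4 × SD² × Z² / (X − Y)², which is exactly the plan's formula. X − Y is therefore the full width of the interval, and the margin is half of it.

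**Step 3: precision delivered at N = 104.**

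- Half-width: 1.96 × 13 / √104 = 25.48 / 10.198 = 2.50
- Full width: 2 × 2.4985 = 5.00
- With the t quantile in place of 1.96: half-width 2.53, full width 5.06, a negligible difference

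**Step 4: what the label would imply if taken literally.**

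N = (1.96 × 13 / 5)² = 649.23 / 25 = 25.97, rounded up to 26. After attrition, 26 / 0.85 = 30.6, so 31. The plan uses neither number.

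**Step 5: recruitment.**

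104 / 0.85 = 122.35. The plan writes 122; rounding up would give 123. Both are covered by the 125 recruited. If 15% of 125 are lost, 125 × 0.85 = 106.25 remain, and with 106 patients the half-width is 1.96 × 13 / √106 = 2.47.

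**Step 6: effect of the SD.**

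The SD in the data may not be 13. For an assumed range of 10 to 16, the half-width at N = 104 runs from 1.96 × 10 / 10.198 = 1.92 to 1.96 × 16 / 10.198 = 3.08. It stays below 5 throughout, so the discrepancy with the label remains on the safe side.

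**Step 7: look for any use of the margin elsewhere.**

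Section 1 names chi-square and Fisher tests for qualitative variables and the Student t test for quantitative ones. Section 1.4 describes yearly progress reports and a final report. None of these compares a result with a margin of 5 or 2.5, and the documents set no success threshold for mean HHS. The margin is used once, to obtain N, and there it is used correctly.

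**The case for a change.** The strongest case for a change is that the wording is wrong in a way anyone can verify, concerns the primary outcome, and would cost one line to correct. The label does offer margin of error as a name for X − Y, and by convention that term is a half-width. The factor of 4 appears in both the symbolic and the numerical formula and is needed to reach 104, so it is not a fault of text extraction. That much stands: half of a two-term label is loose.

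The consequence is weaker than it sounds. The section never writes ±5 or gives any half-width. The second term of the label, precision, has no fixed half-width meaning. The line that sets X to 100 and Y to 95 presents them as the upper and lower ends of an interval, so a reader who works through the section sees that 5 is a length. That line is also the best evidence of what was meant, so deleting it because location does not enter N would make the section less clear.

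Two related arguments do not add to the case:

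- *SD of 13 with a mean between 95 and 100.* If the scale ends at 100, which the documents do not state, an SD of 13 looks large beside a mean near 97.5. It is still attainable: on a 0 to 100 scale the maximum SD at that mean is √(97.5 × 2.5) = 15.6. The section attributes its value to previous studies, which cannot be inspected here, and it does not name 97.5 as the expected mean.
- *Pooled or separate estimate.* The synopsis heads the HHS outcome "Primary Outcome Measure for all study patients", while section 1.1 sizes the stem versions separately. The same phrase heads the secondary outcomes, so it can simply mean that everyone is assessed on the measure. Section 1.1 is clear about what it sizes, namely each group. With 212 evaluable patients (250 less 15%) and a common SD of 13, a pooled mean would have a margin of 1.96 × 13 / √212 = 1.75, which is narrower than the per-group figure.

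**Conclusion.** The concern does not call for a change. Read with its formula and inputs, X − Y = 5 is the full width of the 95% interval for mean HHS at 2 years in one stem group, and the half-width is 2.50 at 104 evaluable patients. The plan's sample size reproduces, and the slip is confined to one term in one definition line.

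Correcting the term would leave the 104 evaluable patients, the 125 recruited per group, the 250 in total and every planned analysis as they are. A literal reading of the label understates the precision of the design, so the error is in the safe direction. The interval reported at the end will be computed from the observed SD and the number of patients assessed, whatever the label says. An analyst who needs to quote the design precision can take ±2.5 per stem version directly from the formula.

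These figures rest on the plan's SD of 13 and the normal approximation. Under the assumed SD range of 10 to 16 the half-width would be 1.92 to 3.08, and the conclusion is the same.

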### 1.2. DETAILED DESCRIPTION OF RANDOMIZATION

NA

### 1.3. HANDLING OF MISSING AND INCOMPLETE DATA

#### 1.3.1. Per Protocol (PP) Population

Patients who have complete data collected per the protocol are the Per Protocol (PP) population.

#### 1.3.2. Intent to Treat (ITT) Population

Patients who have met the Inclusion/Exclusion criteria and have signed the Informed Consent will be tracked. Those patients that dropped-out of the study and did not receive the investigational or control treatment will be accounted with documentation for the specific reason for not receiving the investigational or control device. Accountability for all patients that

have received the investigational or control device but have not completed all follow-up examinations will be tracked using the methods described in "Handling of Missing Data".

### **1.3.3. Sensitivity Analysis**

A sensitivity analysis will be performed to assist in explaining both clinically and statistically the pooling of those patients (ITT population) with missing outcome data with those patients who have complete data collected per protocol (Per Protocol (PP) population). The analysis will compare the study results based on both populations and ensure that the handling of missing data does not cause bias on the overall study conclusion.

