ELIGIBILITY	
Inclusion criteria
 
Patients inclusion criteria for this evaluation are be in accordance with the indications of the GTS® stem and specifically
 
 
Primary osteoarthritis or secondary coxarthritis
 
Inflammation of the hip: rheumatoid arthritis, etc.
 
Femoral neck fracture
 
Avascular necroses of the femoral head
 
Sequelae from previous operations on the hip, osteotomies, etc.
 
Congenital hip dysplasia
 
 
Additional inclusion criteria include:
 
 
18 years of age or older
 
Subjects willing to return for follow-up evaluations
 
Subjects who read, understood study information and provided an informed written consent (specific local regulatory requirements)
 
 
Exclusion criteria
 
Exclusion criteria are in accordance with absolute and relative contraindications for use for GTS® stem
 
Absolute contraindications include:
 
 
Local or systemic infections.
 
Severe muscular, neurological or vascular deficiencies of the extremity involved
 
Bone destruction or poor bone quality that is likely to affect implant stability (Paget's disease, osteoporosis, etc.)
 
Concomitant disease likely to affect implant function
 
Allergy to any of the components of the implant
 
Patients weighing more than 110 kg
 
 
Additional exclusion criteria:
 
 
Subjects unable to co-operate with and complete the study
 
Dementia and/or inability to understand and follow instructions
 
Neurological conditions affecting movement
 
Patient over 18 under law supervision
 

DURATION	The initial study assessment period will be 12 years; 24 months recruitment and the follow-up clinical reviews for all patients will be at 3 months, 1 year, 2 years, 3 years, 5 years, 7 years and 10 years.
-----------------	---

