### **1.3.4. Handling of Missing Data**

It is most important to minimize missing data by retaining patients and obtaining complete data at all required follow-up intervals. According to the Intent Treat (ITT) principle, all patients' missing data will be tracked and treated.

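### Comparing ITT with PP cannot ensure that missing data leave the 2-year mean HHS unbiased, and no other analysis in the plan varies the missing-data assumption

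*Combined protocol and SAP*

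**What the plan says.** The synopsis gives the primary outcome, for all patients, as "Mean Harris Hip Score (HHS) at 2 year postoperative". Section 1 of the SAP puts the analysis on an intent-to-treat basis. Section 1.1 sizes each stem group for the precision of that mean and allows for 15% attrition.

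Four subsections deal with incomplete data:

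- 1.3.1 defines PP by completeness alone: "Patients who have complete data collected per the protocol are the Per Protocol (PP) population". It does not say which visits must be complete. The synopsis schedules reviews at "3 months, 1 year, 2 years, 3 years, 5 years, 7 years and 10 years".
- 1.3.2 describes ITT and refers patients with incomplete follow-up to the section on handling missing data.
- 1.3.3 plans one sensitivity analysis, meant to help explain "the pooling of those patients (ITT population) with missing outcome data with those patients who have complete data collected per protocol". Its stated task is to "compare the study results based on both populations and ensure that the handling of missing data does not cause bias on the overall study conclusion" as well.
- 1.3.4 asks for good retention and then says that "all patients' missing data will be tracked and treated". It gives no method and no assumption about why scores are missing.

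**The concern.** A sensitivity analysis for missing data should show how far the result moves when the assumption about the missing values changes. ITT versus PP does not vary that assumption. It changes who is counted, and perhaps adds one unspecified way of filling gaps. The 2-year means of the two populations could agree closely whether the patients lost are typical or quite different from those seen.

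This is the only check the plan offers on a loss that it expects to be 15%. Good retention reduces the problem but does not test for it. A final report following 1.3.3 as written could present agreement between ITT and PP as proof that the primary mean is unbiased. The study has no control arm and states no HHS threshold, so what is exposed is the accuracy of the reported mean and its confidence interval.

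**Working it through.** **Inputs from section 1.1:** SD 13, Z = 1.96, X − Y = 5, attrition 15%, 125 per stem group. **Assumed:** the difference d between the mean of patients with a 2-year HHS and the mean of those without. The documents give neither its size nor its direction.

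**Step 1. Reproduce the plan's figures.** N = 4 × 13² × 1.96² / 5² = 103.9, so 104, as stated. 104/0.85 = 122.4; the plan gives 122 and rounds up to 125. Because of the factor 4, X − Y is the full width of the interval: the half-width is 1.96 × 13/√104 = 2.50 points.

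**Step 2. What the comparison can see.**

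*ITT on observed scores.* A patient with no 2-year HHS is in neither mean. The two means can differ only through patients who have a 2-year score but lack other data. A gap there may hint that attendance is related to score, but agreement does not show that the unseen scores resemble the seen ones.

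*ITT with values imputed from observed scores.* Suppose PP is everyone with a 2-year score, and missing scores are imputed by regression on an earlier HHS that has correlation r with the 2-year HHS and an equal SD. Let a fraction k of the difference d be visible in the earlier score. Then

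- gap, PP minus ITT = 0.15 × r × k × d
- bias left in the ITT mean = 0.15 × d × (1 − r × k)

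With d = 10 and r = 0.5 (both assumed):

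- k = 0: gap 0, remaining bias 0.15 × 10 = 1.5
- k = 0.5: gap 0.15 × 0.5 × 0.5 × 10 = 0.375, remaining bias 1.5 × 0.75 = 1.125

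The gap shows the predictable part of the bias, and the rest stays hidden. A simulation (20,000 trials of 125 patients, 15% missing, values imputed from the observed distribution) gave an average ITT–PP gap of about zero for d = 0, 10 and 20, while the bias was about 0, 1.5 and 3.0 points. In that setting the check gives the same answer with no bias as with 3 points of it.

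**Step 3. Size of an undetected bias.** The full-cohort mean equals the observed mean minus 0.15 × d, so the bias is b = 0.15 × d. Observed per group: 125 × 0.85 ≈ 106. SE = 13/√106 = 1.263. Coverage of the nominal 95% interval = Φ(1.96 − b/SE) − Φ(−1.96 − b/SE).

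| d (assumed) | b | b as share of 2.5 | b/SE | Coverage |
|---|---|---|---|---|
| 5 | 0.75 | 30% | 0.59 | 91% |
| 10 | 1.50 | 60% | 1.19 | 78% |
| 15 | 2.25 | 90% | 1.78 | 57% |
| 20 | 3.00 | 120% | 2.38 | 34% |

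The bias equals the planned half-width at d = 2.5/0.15 = 16.7 points. If missing patients score higher, the sign of the bias reverses and the coverage is the same.

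**The case against.** Reporting ITT beside PP is common practice, and *ensure* may be meant only as an aim: to check that the conclusion holds in both populations. That is a fair reading of intent, and the comparison can stay as supportive information. But the sentence still assigns it a task it cannot perform, and nothing else in the plan performs that task.

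A reader might infer that the comparison is uninformative, or that it must fail however missing scores are handled. The documents support neither. A gap can signal that attendance is related to score, and imputation from earlier scores can reveal the predictable part of the bias. The wording in 1.3.4 is also open enough to cover a fixed unfavourable score, in which case ITT versus PP would bound the bias in one direction. The plan specifies no such rule, so no credit can be taken for it, but the point must be confined to observed-score analysis and imputation from observed scores.

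It can also be said that the gap in 1.3.4 is the root of the problem. In part, yes. Yet naming a method there would not be enough: if it imputes from observed scores, 1.3.3 would still lack an analysis that varies its assumption.

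Finally, the lowest coverage figures need a large difference: 20 points is about 1.5 of the plan's SDs (20/13). At 5 points the bias is 0.75, well inside the planned half-width. This stands, and is why the whole range is shown.

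**Conclusion.** The point holds in this limited form and should be fixed. The assurance in 1.3.3 does not follow from the analysis planned there: whether ITT uses observed 2-year scores or imputes from observed scores, agreement with PP does not exclude bias linked to the unseen score. This is a matter of logic and needs no assumed number.

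The size does rest on assumptions. At the planned 15% loss, assumed differences of 5 to 20 points in either direction give a bias of 0.75 to 3.0 points and per-group coverage of about 91% down to 34%, taking the SD as 13 and the mean as approximately normal.

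A reader might go on to infer that the 2-year mean will be biased, or that a success decision could be overturned. The documents support neither: they say nothing about how lost patients score, and with no control arm and no HHS threshold there is no decision to overturn. The 2.5 points is a planning precision, not a limit for action. The harm is misplaced confidence in the reported mean and interval, so the weight is moderate.

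**What to change.** 1. In 1.3.4, state the primary analysis of the 2-year mean HHS as multiple imputation or a repeated-measures model under missing at random, using the HHS values actually collected and stem version, and state that assumption.
2. In 1.3.3, add a delta-adjusted analysis that shifts the imputed 2-year scores over a pre-stated range, for example 5, 10, 15 and 20 points in both directions, and reports the mean and 95% CI at each shift. At 15% missing, these shifts move the mean by 0.75, 1.5, 2.25 and 3.0 points.
3. Define PP for the 2-year endpoint without requiring later visits, and report ITT versus PP as supportive only.
4. In 1.3.3, change *ensure* to *assess*.

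The cost is SAP wording and modest extra analysis, with no new visits or patients. The interval may be slightly wider than one from observed scores alone, and the mean may shift in either direction. Rules for hips revised before 2 years and for two hips in one patient are separate points and are not part of this change.

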### **1.3.4. Handling of Missing Data**

It is most important to minimize missing data by retaining patients and obtaining complete data at all required follow-up intervals. According to the Intent Treat (ITT) principle, all patients' missing data will be tracked and treated.

## **1.4. DATA ANALYSES**

### **1.4.1. Interim analysis**

Annual Progress Report - The evaluator must submit a yearly progress report to Biomet and the ethical committee summarizing his preliminary clinical results.

### **1.4.2. Final**

Final Report - The evaluator must make a final report of his clinical results upon completion of the evaluation. This report is submitted to Biomet and the ethical committee. The data from all evaluations will be collected and final Report will be produced; all evaluators shall sign this report, or if any evaluator does not sign a justification shall be provided.
